# 14 SHIPPING OF URINARY KERATAN SULFATE AND IMMUNE RESPONSE SAMPLES

Urine samples collected to monitor uKS may be assayed at the participating Registry site as per the institutions' laboratory guidelines and procedures and/or at BioMarin's designated laboratory. Serum samples to monitor immune response will be assayed by BioMarin's designated laboratory.

# 15 DATA SOURCES

The Registry database maintained by BioMarin or designated vendor will collect data from all participating sites. Study site personnel at participating sites will directly enter assessments' results into the database. The validity of the data will be monitored by audit and comparing to source documents as described in Section 16.2 and Section 19. Statistical analyses will be performed as described in Section 18 and the SAP.

#### 16 DATA MANAGEMENT

#### 16.1 Patient Identification

All patient information is strictly confidential. Each patient will be identified by a unique patient identifier. Patients will not be identified by name for the purposes of data collection. In legal jurisdictions where the use of initials is not permitted, a substitute identifier will be used.

# 16.2 Case Report Forms and Source Documents

The Electronic Case Report Forms (eCRFs) must be completed using a web-based application developed and validated by BioMarin or designee. Study site personnel will be trained on the application and will enter the clinical data from source documentation. Unless explicitly allowed according to the eCRF instructions, blank data fields are not acceptable.

In the event of an entry error, or if new information becomes available, the site personnel member will correct the value by deselecting the erroneous response and then selecting or entering the factual response. In compliance with the US Code of Federal Regulations (CFR) 21 CFR §11, the system will require the site personnel member to enter a reason for changing the value. The documented audit trail will include the reason for the change, the original value, the new value, the time of the correction, and the identity of the operator.

BioMarin's policy is that study data on the eCRFs must be verifiable to the source data, which necessitates access to all original recordings, laboratory reports, and patient records. In addition, all source data should be attributable (signed and dated). The Investigator must therefore agree to allow direct access to all source data. Patients (or their legally authorised representatives) must also allow access to their medical records, and patients will be informed of this and will confirm their agreement when giving informed consent. If an Investigator or Institution refuses to allow access to patient records because of confidentiality, arrangements must be made to allow an "interview" style of data verification.

A CRA designated by BioMarin will compare the eCRFs with the original source documents at the study site and evaluate them for completeness and accuracy before designating them as "Source Data Verified." If an error is discovered at any time or a clarification is needed, the CRA or designee will create an electronic query on the associated field. Site personnel will then answer the query by either correcting the data or responding to the query. The CRA will then review the response and determine either to close the query or re–query the site if the response does not fully address the question. This process is repeated until all open queries have been answered and closed.

# Morquio A Registry Study (MARS)

Page 54

Detailed procedures for data collection and submission will be provided to participating sites in the SRM.

#### 17 RETENTION OF RECORDS

The Investigator must retain all study records required by BioMarin and by the applicable regulations in a secure and safe facility. The Investigator must consult a BioMarin representative before disposal of any study records, and must notify BioMarin of any change in the location, disposition, or custody of the study files. The Investigator/Institution must take measures to prevent accidental or premature destruction of essential documents, i.e., documents that individually and collectively permit evaluation of the conduct of a study and the quality of the data produced, including paper copies of study records (e.g., patient charts) as well as any original source documents that are electronic as required by applicable regulatory requirements.

The Investigator/Institution should retain patient files and other source data in accordance with the country-specific regulatory requirements for data retention. BioMarin must be notified and will assist with retention should the Investigator/Institution be unable to continue maintenance of patient files for the term required. BioMarin is responsible for informing the Investigator/Institution as to when these documents no longer need to be retained.

#### 18 DATA ANALYSIS

# 18.1 Statistical and Analytical Plans

A SAP will provide full details of analyses and will be finalized prior to data analysis.

# 18.1.1 Study Dosage and Administration

Enrolled patients may have access to treatment of Vimizim, and such treatment information may be recorded by study personnel at the Registry sites. Based on the available data, the total number of doses received, total duration of exposure, and mean weekly dose may be presented by treatment groups using summary statistics such as n, mean, SD, median, minimum, and maximum.

# **18.1.2** Sample Size Determination

All MPS IVA patients will be invited to enrol in the Registry, assuming all regulatory requirements are met for sites that have agreed to participate, in countries where marketing authorisation has been granted.

The sample size of the study is not determined by statistical power consideration, as no statistical hypotheses are posed.

# 18.1.3 Interim Analysis

In addition to annual reporting, interim analyses will be conducted to support regulatory health authority commitments.

# 18.1.4 General Analysis Considerations

Descriptive summaries of continuous variables will include the mean, SD, median, range, and 95% confidence interval and/or inter-quartile range when appropriate. Descriptive summaries of categorical variables will include n and percent. When possible/applicable graphical summary statistics over time and/or summary statistics accounting for time will be utilized.

Statistical tests will be two-sided at the 0.05 level, unless otherwise specified. All confidence intervals will be two-sided 95% confidence intervals, unless otherwise specified. All statistical tests and associated p-values will be considered nominal. See Section 11.1 for definitions of timepoints.

# 18.1.5 Analysis Populations

# 18.1.5.1 Safety Population

The Safety Population will consist of all patients who receive at least 1 dose of Vimizim at or after registry entry.

#### 18.1.5.2 Full Analysis Set Population

The Full Analysis Set will consist of all patients diagnosed with MPS IVA who provide written, signed informed consent or, in the case of patients aged <18 years, those for whom written assent (if required) and written informed consent by a legally authorised representative are provided.

# 18.1.5.3 Treatment Groups

ERT-naïve patients are defined as the group of patients who had never received Vimizim either prior to the Registry enrolment, or during Registry participation. ERT-treated patients are defined as the group of patients who had received at least 1 dose of Vimizim either prior to the Registry enrolment, or during Registry participation. Time on ERT treatment (defined as ERT infusion date +7 days) and not on treatment during follow-up will be identified.

Analysis of clinical outcomes, demographic and baseline characteristics will be conducted, stratified by the 2 treatment groups (ERT-naïve patients vs ERT-treated patients). Due to the observational nature of the Registry, ERT-treated patients may discontinue treatment. Treatment discontinuation will be defined based on the stop date reported in the enzyme replacement log plus 7 days (to include events potentially occurring 'on treatment' before the next anticipated infusion, if the date of last infusion was the documented stop date). Outcome analyses among the ERT-treated will generally be censored at the time of discontinuation (i.e. an 'as treated' analysis). Exceptions to this convention will be detailed in the SAP.

If there are significant numbers of patients who discontinue treatment and re-initiate, sensitivity analysis may be performed by describing outcomes during the period of re-initiation.

# 18.1.6 Handling of Dropouts and Missing Data

Patients who discontinued the Registry prematurely will not be replaced. The following missing data imputation rules will apply to all analyses unless otherwise specified elsewhere in the SAP. Missing dates or partially missing dates will be imputed conservatively for concomitant medications and AEs to ensure that an AE is considered treatment emergent and has the longest possible duration. Data in regards to reason for drop out or discontinuation of the Registry will be analysed.

# 18.1.7 Safety and Clinical Outcome Analysis

Separate data analyses of the MOR-005 and MOR-007 Substudies will be performed per the MOR-005 and MOR-007 Substudy SAPs. For the MOR-005 Substudy analyses, data from the MOR-005 substudy will be combined with data from the MOR-005 clinical study. A similar analysis will be provided for the MOR-007 Substudy data.

Analyses performed to address the objectives of this study will consider both clinical outcome variables and safety variables. The clinical outcome variables include endurance tests (6MWT and 3MSCT), anthropometric measurements, urine KS concentration (normalized to creatinine), respiratory function tests, number of respiratory infections, assisted breathing history, duration and number of times CPAP or BiPAP was used during the year, echocardiograms, surgeries, quality of life assessments (EQ-5D-5L test in all patients, MPS Health Assessment Questionnaire for MOR-005 Substudy patients only, PedsQL for MOR-007 Substudy patients only), ophthalmologic assessments, audiometric assessments, liver and spleen assessments, progression of skeletal deformities, frequency and time to orthopaedic surgeries, and Tanner Series/Scales. The safety variables include AEs, concomitant medications, occurrence of BMT/HSCT, clinical laboratory tests, vital signs, ECGs, echocardiograms, immunogenicity results, physical examinations, imaging studies, and cervical spine imaging.

# Objective 1: To characterize and describe the MPS IVA population as a whole, including the heterogeneity, progression, and natural history of MPS IVA.

In order to characterise and describe the MPS IVA population as a whole, clinical outcomes variables as specified in Table 8.1.1.1 and demographics will be summarised in the 12 months prior to or 90 days after Registry Entry (for consistency with data entry at Registry Entry) stratified by ERT status at Registry Entry. The measurement closest to Registry Entry during this period will be used to describe patients. The natural history and progression of MPS IVA will be described in ERT-naïve and ERT-treated patients based on measurements while not on ERT treatment (i.e. all measurements for ERT-naïve and prior to index for ERT-treated), with progression of the disease based on measurements of clinical outcomes described over time and presented by age.

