#### 3.7 Data Sources

Investigators treating MPS IVA patients are encouraged to participate in the Registry by enrolling patients and entering all data from these assessments outlined in the Data Elements of Interest (Table 8.1.1.1) into the Registry database. Data may be collected for all or some of the assessments as outlined in Section 8.1.1 and Table 8.1.1.1, dependent upon the individual's current SOC, and whether or not the patient is receiving treatment for MPS IVA such as Vimizim, hematopoietic stem cell transplant (HSCT), or bone marrow transplant (BMT).

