#### 8 RESEARCH METHODS

# 8.1 Study Design

The MARS is a multicentre, multinational, observational Registry for patients with MPS IVA disease, intended to characterise and describe the MPS IVA population as a whole, including the heterogeneity, progression, and natural history of MPS IVA, and to track the safety and clinical outcomes of patients with MPS IVA treated with Vimizim. The data collected by the Registry are intended to enable better characterization of the natural history of MPS IVA and to track patients' clinical responses to various therapies. All patients with a confirmed diagnosis of MPS IVA disease may be eligible to participate in this Registry. Patients are not required to receive Vimizim to be eligible to participate in this Registry.

In addition, this Registry will collect additional data on patients who have completed the MOR-005 and MOR-007 clinical trials through 2 Substudies of this Registry. Patients enrolled in the MARS who previously participated in the MOR-005 and MOR-007 clinical studies will be enrolled into the appropriate Substudy (MOR-005 or MOR-007) for a minimum of 5 years from the time of the patient's enrolment in the MOR-005 clinical study or MOR-007 clinical study. After this 5-year period, these patients should remain in the MARS until the Registry is complete. Patients initially enrolling into 1 of the Substudies will give their consent to participate in both the applicable Substudy and to continue participation in the MARS Registry, following the completion of the respective Substudy, by signing an IRB/IEC/REB-approved ICF/PIAF and assent, if applicable, for both the relevant Substudy and the MARS Registry. Patients who become pregnant and are taking Vimizim may also participate in a pregnancy sub-study (see Section 13).

Investigators are encouraged to record data in line with the Data Elements of Interest, which includes assessments that are currently used to monitor MPS IVA-related clinical manifestations and to stage disease progression across the life-long course of the disease. Data may be collected for all or some of the assessments as outlined in Section 11 and Table 8.1.1.1, dependent upon the individual's current SOC, and whether or not the patient has received treatment for MPS IVA such as Vimizim, HSCT, or BMT.

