#### **8.3.3** Exclusion Criteria

Patients who meet the following exclusion criterion will not be eligible to participate in the Registry or Registry Substudies:

• Currently participating in a BMN 110 (elosulfase alfa) clinical trial.

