# 11.25 Occurrence of Hematopoietic Stem Cell Transplant/Bone Marrow Transplant

If a patient has received a HSCT or BMT prior to enrolment into the Registry, Investigators may report this by entering data into the Registry database. If the transplantation occurs during the patient's participation in the Registry, this would be considered a reportable serious adverse event (SAE) if the patient is receiving Vimizim (Section 22) and should be reported to BPV in addition to entry into the Registry database.

Information on occurrence of HSCT/BMT may be collected at timepoints indicated in the Data Elements of Interest (Table 8.1.1.1). Additional details are provided in the SRM.

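### Post-transplant measurements can enter the natural-history description, because Objective 1 screens out Vimizim exposure but not HSCT or BMT

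*Protocol*

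**What the plan says.** Protocol Section 18.1.7, Objective 1, describes natural history and progression from measurements taken off ERT, which it spells out as "all measurements for ERT-naïve and prior to index for ERT-treated". Section 18.1.5.3 fixes the group: "ERT-naïve patients are defined as the group of patients who had never received Vimizim either prior to the Registry enrolment, or during Registry participation". No other therapy enters that definition.

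Elsewhere the protocol treats transplantation as disease treatment. Section 8.1 makes data collection depend partly on "whether or not the patient has received treatment for MPS IVA such as Vimizim, HSCT, or BMT", and Section 3.7 has similar wording. The only exclusion criterion in Section 8.3.3 is "Currently participating in a BMN 110 (elosulfase alfa) clinical trial", so transplanted patients may enrol. Section 11.25 covers transplants before entry ("If a patient has received a HSCT or BMT prior to enrolment into the Registry, Investigators may report this by entering data") and during participation, where the transplant is a reportable SAE if the patient is receiving Vimizim. Table 8.1.1.1 lists occurrence of HSCT/BMT at entry and every 6 months.

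In the analysis sections, BMT/HSCT is named only among the safety variables of Section 18.1.7. Objective 4 covers other treatments by counts, frequencies and listings. It adds an effectiveness summary only for a treatment that is indicated for MPS IVA and used in more than 5% of the Registry population.

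For Objective 2, the effectiveness window runs from baseline to Vimizim discontinuation or end of follow-up. Section 18.1.5.3 says outcome analyses are generally censored at discontinuation (logged stop date plus 7 days) and leaves exceptions to the SAP.

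**The concern.** A natural-history description should show the disease without treatment that may alter its course. The plan applies that principle to one treatment only. An ERT-treated patient contributes nothing after first Vimizim exposure, even if Vimizim is later stopped and the patient is again off ERT. A patient who has had HSCT or BMT, which the protocol also calls treatment for MPS IVA, contributes every measurement until Vimizim starts, or all of them if it never does.

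At stake is what Objective 1 can claim. If transplant changes growth, endurance, respiratory function or surgery rates in either direction, the age-based progression summaries blend two disease courses under one label. Others may use those summaries as an untreated reference. Objective 2 carries a lesser form of the same question, because its default window does not stop at transplant.

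**Working it through.** The protocol states no sample size, transplant count or effect size for this point, so there is no figure to reproduce. The check traces what the written rules do with each kind of transplanted patient.

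| Patient | Objective 1 natural history | Objective 2 effectiveness |
|---|---|---|
| Never Vimizim, transplant before entry | ERT-naïve, so all measurements included, post-transplant ones too | Not in the ERT-treated group |
| Never Vimizim, transplant during the Registry | Same; Section 11.1 runs follow-up to the last data point | Not in the ERT-treated group |
| Transplant, then Vimizim | Measurements between transplant and index precede index, so included | Included, and not separated by default |
| On Vimizim, transplant, Vimizim continues | Nothing after index is used | Post-transplant values inside the default window |
| On Vimizim, Vimizim stopped at transplant | Nothing after index is used | Censored at stop date plus 7 days |

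The first three rows show the gap in Objective 1. It follows from an affirmative inclusion rule, which, unlike the Objective 2 censoring convention, has no qualifier and no pointer to SAP exceptions. Rows three and four are what remains for Objective 2; row five is already handled.

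**Can a size be given?** Let h be the transplanted share of the Registry, q the ERT-naïve share, g the share of transplanted patients who are ERT-naïve, and c the share of ERT-treated patients with pre-index data. None of the four is in the protocol, so the values below are assumptions.

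- Transplanted share of the ERT-naïve group = h × g / q.
- Even spread (g = q): the share equals h, so h = 1% to 5% gives 1% to 5%.
- All transplanted patients ERT-naïve (g = 1), with q from 10% to 50%: lowest 0.01 / 0.50 = 2%, highest 0.05 / 0.10 = 50%.

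The natural-history cohort is not the ERT-naïve group, because it also takes pre-index data from ERT-treated patients. With g = 1, the transplanted share of contributing patients is h / (q + c(1 − q)). For q = 20%:

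- c = 0: 0.01 / 0.20 = 5% to 0.05 / 0.20 = 25%.
- c = 1: 0.01 / 1 = 1% to 0.05 / 1 = 5%.

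The answer moves several-fold with quantities nobody can read from the protocol, and h itself could be close to zero. The arithmetic supports one limited statement: a treatment below the 5% Registry-wide threshold in Objective 4 may still be a larger share of the natural-history data.

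**The case against.** **Natural history need not mean untreated.** Objective 1 speaks of being off ERT, and Section 6.2 refers to natural history in treated and untreated patients alike. That is fair as to wording. It does not rescue the rule, because Objective 1 itself sets out to use only off-treatment data and then recognises a single treatment.

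**The transplants are visible.** They are a data element, a safety variable and, if counted among other treatments that affect outcomes, part of the Objective 4 listings. This stands, and it limits the harm: a reader could see how many patients are involved. It does not separate their outcomes from the Objective 1 summaries.

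**The analyses are descriptive.** No hypotheses are posed and p-values are nominal (Sections 18.1.2 and 18.1.4). That lowers the stakes, but a descriptive summary can still mislabel what it describes.

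**Objective 2 belongs to the SAP.** This largely stands. Section 18.1.5.3 says censoring is generally at discontinuation and defers exceptions, Section 18.1.8 lets the SAP prevail, and a patient who stops Vimizim at transplant is censored anyway. A reader might infer that transplant effects will be credited to Vimizim. The protocol does not establish that, because the SAP is not shown and may contain a transplant rule.

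**The size is speculative.** This stands in full. A reader might infer that 5% to 25% of the natural-history cohort has been transplanted. That range needs assumed values for h and q, the premise that all transplanted patients are ERT-naïve, and the ERT-naïve group as the sole denominator. No section supports the premise, and Section 11.25 explicitly foresees transplant in a patient receiving Vimizim.

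**Conclusion.** The point holds for Objective 1. Under the rule as written, post-transplant measurements can enter the natural-history description, both for patients who never received Vimizim and for those transplanted before index. The conclusion rests on the definitions alone and needs no assumption about numbers.

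How far the results would be affected, and in which direction, cannot be stated. That depends on the share of contributing measurements taken after transplant and on how far the course after transplant differs from the untreated course; the protocol gives neither. If no enrolled patient has had a transplant, nothing changes.

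For Objective 2 the conclusion is weaker: the default window does not end at transplant, but the protocol leaves room for an exception. That warrants a sensitivity analysis, not a finding that the primary effectiveness analysis is wrong. Overall this is an inexpensive improvement worth making, and the protocol does not show a demonstrated bias.

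**What to change.** **Objective 1, Section 18.1.7.** Limit natural-history measurements to those before index and before any recorded HSCT or BMT. A patient transplanted before entry would then contribute only pre-transplant historic data, if any. Report the number of patients and measurements this removes, and present post-transplant data under Objective 4, as a listing where its conditions for an effectiveness summary are not met. The snapshot of the whole population at Registry Entry can stay as it is.

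**Objective 2.** Add one sensitivity analysis that censors at HSCT or BMT and omits patients transplanted before index, unless the SAP already has an equivalent rule.

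Because Section 18.1.8 gives the SAP precedence, the SAP should carry the same wording.

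**Cost.** A few sentences, the loss of a few measurements, and one data check. The protocol names the occurrence of transplant as a data element, and Section 11.25 makes reporting of a prior transplant optional for the investigator. The sponsor should confirm that the transplant date is captured and query sites where it is missing. Until then the restriction is only as complete as the reporting, and the results should say so.
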